1. VERSION HISTORY

Table 1. Summary of Changes

Version/ Date	Associated Protocol Amendment	Rationale	Specific Changes
1 27 Oct 2021	Original 29 Jul 2021	N/A	N/A

NOTE: *Italicized* text within this document has been taken verbatim from the Protocol.

2. INTRODUCTION

This study will evaluate the effect of PF-06650833 on pharmacokinetics of oral contraceptive (OC) steroids, in order to select appropriate contraception requirements in Phase 2 studies.

CCI

This statistical analysis plan (SAP) provides the detailed methodology for summary and statistical analyses of the data collected in Study B7921026. Any major modifications of the primary endpoint definition or its analysis will also be reflected in a protocol amendment.

2.1. Study Objectives, Endpoints, and Estimands

Objectives	Endpoints
Primary:	Primary:

 To estimate the effect of multiple oral doses of PF-06650833 on the PK of a single dose of a combination OC in healthy female participants. 	
 C_{max} and AUC_{last} of EE and LN.
Secondary:	Secondary:

 To evaluate the safety of PF-06650833 when co-administered with a single dose of a combination OC in healthy female participants. 	
 Safety: laboratory tests, AEs reporting and vital signs.
Tertiary/Exploratory:	Tertiary/Exploratory:

 To characterize the PK of a single dose of a combination OC with or without PF-06650833 in healthy female participants. 	
 T_{max}, and if data permit CL/F, t_{1/2} and AUC_{inf} of EE and LN.

2.2. Study Design

This is a Phase 1, fixed-sequence, multiple-dose, open-label study of the effect of multiple dose PF-06650833 on single dose OC PK in healthy female participants. A total of approximately 10 healthy female participants will be enrolled in the study. The study will consist of 2 periods in a single fixed sequence. Participants will be screened within 28 days of the first dose of investigational product in Period 1. Participants will report to the CRU the day prior to Day 1 dosing in Period 1. Participants will remain in the CRU for a total of 16 days and 15 nights. There will be no washout period.

[figure not shown]
On Period 1 Day 1, participants will be dosed with a single administration of OC in the form of 1 PORTIA® (EE and LN) or equivalent tablet, orally. OC (EE and LN) PK will then be assessed at pre-dose and over 48 hours, post OC dosing. Period 1 will be immediately followed by Period 2 with no washout, in which participants will be dosed orally with PF-06650833 400 mg MR QD for 9 days followed by administration of a single dose of OC on the morning of Day 10. OC PK will be assessed at pre-dose and for 48 hours following OC dosing. On Day 10, the morning dose of PF-06650833 and the single OC dose will be administered simultaneously within 5 minutes. Dosing with PF-06650833 400 mg PO QD will continue until Day 11 (Table 2). Participants will be discharged on Day 12 only after review of safety laboratory by the PI. [Figure 1](#) shows the schematic of Study Design.

Table 2. Study Design and Treatments

Period 1	Washout	Period 2
Treatment R	None	Treatment T

Treatment R: Single dose of OC in the form of 1 PORTIA® (EE and LN) or equivalent oral tablet, containing EE 30 µg and LN 150 µg.

Treatment T: Single dose of combination OC in the form of 1 PORTIA® (EE and LN) or equivalent oral tablet, containing of EE 30 µg and LN 150 µg on the morning of Day 10 following 9 days of PF-06650833 dosed at 400 mg PO QD. Dosing with PF-06650833 at 400 mg PO QD will continue through until Day 11.

Figure 1. Schematic of Study Design

3. ENDPOINTS AND BASELINE VARIABLES: DEFINITIONS AND CONVENTIONS

3.1. Primary Endpoints

C_{max} and AUC_{last} of EE and LN.

3.2. Secondary Endpoints

- Laboratory tests.
- Adverse events.
- Vital signs.

3.3. Tertiary/Exploratory Endpoint(s)

T_{max} , and if data permit CL/F, $t^{1/2}$ and AUC_{inf} , of EE and LN.

3.4. Baseline Variables

The following baseline variables will be summarized for each treatment. Details of summary analyses are described in [Section 6](#).

Demographic characteristics:

- Baseline age.
- Gender (female vs. male).

- Race (white, black, Asian, other).
- Baseline body weight.
- Baseline Body Mass.

The baseline data measured at Day 1 are:

- Medical history & demography, medication history.
- Physical Examinations.

For laboratory data, baseline for the "PF+OC" phase is defined as the last measurement collected before administering the first dose of OC at the beginning of Period 2 (ie, P2D10 pre-dose).

For vital signs data, baseline for the "PF-only" phase is defined as the last measurement collected before administering the first dose of PF at the beginning of Period 2 (ie, P2D1 pre-dose), and baseline for the "PF+OC" phase is defined as the last measurement collected before administering the first dose of OC at the beginning of Period 2 (ie, P2D10 pre-dose).

For ECG data, baseline for the "PF+OC" phase is defined as the last measurement collected before administering the first dose of OC at the beginning of Period 1 (ie, P1D1 pre-dose).

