3.5.1. Adverse Events

An adverse event will be considered a Treatment-Emergent Adverse Event (TEAE) if the event started during the effective duration of treatment. All events that start on or after the first dosing day and time/start time, if collected, but before the last dose plus the lag time (28 days) will be flagged as TEAEs. The algorithm will not consider any events that started prior to the first dose date. Any events occurring following start of treatment or increasing in severity and occur in either of the following three phases: OC, PF-06650833 (Days 1-10 of

Period 2), OC+PF-06650833 (Days 10-12 of Period 2), will be counted as treatment emergent. Events that occur in a non-treatment period (for example, Follow-up) will be counted as treatment emergent and attributed to the previous treatment taken.

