3.5.2. Laboratory Data

Safety laboratory tests will be performed as described in the protocol.

To determine if there are any clinically significant laboratory abnormalities, the haematological, clinical chemistry (serum) and urinalysis safety tests will be assessed against the criteria specified in the sponsor reporting standards. The assessment will take into account whether each participant's baseline test result is within or outside the laboratory reference range for the particular laboratory parameter.

Plot of laboratory parameter(s) value and plot of change from baseline may be requested for parameters changing significantly from baseline.

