5.2. General Methods

To assess any effect of PF-06650833 on EE or LN exposures, natural log transformed AUC_{last} and C_{max} will be analyzed using a mixed effects model with treatment as a fixed effect and participant as a random effect. Estimates of the adjusted mean differences (Test-Reference) and corresponding 90% CIs will be obtained from the model and will be exponentiated to provide estimates of the ratio of adjusted geometric means (Test/Reference) and 90% CIs for the ratios.

The following assessment should be performed:

- Effect of PF-06650833 on OC (EE or LN) exposures with OC alone (Period 1 Day 1 PK) as the Reference treatment and co-administration of PF-06650833 and OC (Period 2 Day 10 PK) as the Test treatment.*

Data will be presented – ie, listed and summarized – by treatment/period and overall. Continuous data will be summarized comprising mean, median, standard deviation, minimum and maximum. Categorical and binary data that are summarized will be via percentages. Some measures will be summarized using graphical representations by treatment/period, where appropriate.

The assignment of the reference and test treatment for drug-drug interaction evaluation is shown in Table 4.

Table 4. Assignment of Reference and Test Treatments

Reference Treatment (Observation Time)	Test Treatment (Observation Time)
OC (EE+LN) (PERIOD 1/DAY 1)	PF-06650833 + OC (EE+LN) (PERIOD 2/DAY 10)

Table 5. Calculation and Safety Reporting by Treatment

Treatment Code	Treatments	PK Calculation	Safety reporting
R	OC (EE and LN)	Day 1 PK in Period 1	Period 1
T	OC (EE and LN) + PF-06650833	Day 10 PK in Period 2	Period 2

For summary statistics, median and mean plots by sampling time, the nominal PK sampling time will be used, for individual participant plots by time, the actual PK sampling time will be used.

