6.2. Safety Summaries and Analyses

All safety analyses will be performed on the safety population and summarized in accordance with Pfizer Data Standards.

All clinical AEs, SAEs, TEAEs, withdrawal due to AEs, ECGs, vital signs and safety laboratory data will be reviewed and summarized on an ongoing basis during the study to evaluate the safety of participants.

Safety data will be summarized descriptively through appropriate data tabulations, descriptive statistics, categorical summaries, and graphical presentations, where appropriate. Categorical outcomes (eg, AEs) will be summarized by participant counts and percentage. Continuous outcome (eg, blood pressure, pulse rate, etc.) will be summarized using N, mean, median, standard deviation, etc. Change from baseline (CFB) in laboratory data, and vital signs will also be summarized. Participant listings will be produced for the safety endpoints accordingly.

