6.2.2. Laboratory Data

Laboratory data will be listed and summarized by treatment in accordance with the sponsor reporting standards. Baseline is as defined in [Section 3.5.2](#).

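### The SAP defines no laboratory baseline before PF-06650833 starts, so its change-from-baseline tables miss any laboratory effect already present by Period 2 Day 9/10

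*SAP*

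**What the plan says.** Laboratory tests are a named secondary endpoint (Protocol Section 3; SAP Sections 2.1 and 3.2). SAP Section 6.2 commits to change-from-baseline summaries: "Change from baseline (CFB) in laboratory data, and vital signs will also be summarized".

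SAP Section 3.4 defines baselines by data type:

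- **Laboratory:** "For laboratory data, baseline for the 'PF+OC' phase is defined as the last measurement collected before administering the first dose of OC". The sentence goes on to place this at Period 2 Day 10 pre-dose. No other laboratory baseline is given.
- **Vital signs:** two baselines. One is the Period 2 Day 10 pre-dose value. The other is Period 2 Day 1 pre-dose: "baseline for the 'PF-only' phase is defined as the last measurement collected before administering the first dose of PF".
- **ECG:** the last value "before administering the first dose of OC at the beginning of Period 1 (ie, P1D1 pre-dose").

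Section 3.5.1 assigns adverse events to one of several phases, "in either of the following three phases: OC, PF-06650833 (Days 1-10 of" Period 2) and the combination, so PF-06650833 alone is recognised as a safety phase. In Table 5 (Section 5.2), the treatment T row pairs "Day 10 PK in Period 2" for PK with the whole of Period 2 for safety reporting.

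Section 3.5.2 says the abnormality assessment considers whether the "baseline test result is within or outside the laboratory reference range for the particular laboratory parameter", without saying which baseline. Section 6.2.2 says "Laboratory data will be listed and summarized by treatment in accordance with the sponsor reporting standards" and refers to Section 3.5.2 for the baseline. Section 3.5.2 defines no time point.

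**The concern.** The Period 2 Day 10 pre-dose value is taken on PF-06650833. It is a sensible reference for what changes when the contraceptive is added, but nothing accompanies it to describe what changed between the drug-free state and that point. The change tables would cover only the last few days of PF-06650833 dosing. Someone reading a small mean change there could take it to mean that laboratory values barely moved on the drug, when they may have moved fully before the reference sample was drawn.

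The same gap affects the abnormality assessment. A programmer who follows Section 6.2.2 to Section 3.5.2 finds no definition. One who turns to Section 3.4 finds only an on-drug value, and a participant pushed out of range by PF-06650833 before Day 10 could then be classed as out of range at baseline.

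**Working it through.** The plan states no figure for this point, so there is none to reproduce. The check sets the baseline definitions against the dosing days and the laboratory schedule.

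**Inputs**

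- PF-06650833 is given once daily from Period 2 Day 1 through Day 11, which is 11 doses. The contraceptive is given on Period 1 Day 1 and Period 2 Day 10 (Protocol Section 4.1; SAP Section 2.2).
- Safety laboratory samples, read by column position in the Protocol Section 1.3 schedule: screening, Day -1, and Period 2 Days 9, 11 and 12. Column alignment in the extracted table is not certain. The conclusion does not depend on it, because Day 9 and Day 10 are both on drug.

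**Baselines side by side (SAP Section 3.4)**

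| Data | Before PF-06650833 | On PF-06650833 |
|---|---|---|
| Vital signs | Period 2 Day 1 pre-dose | Period 2 Day 10 pre-dose |
| ECG | Period 1 Day 1 pre-dose | none |
| Laboratory | **none** | Period 2 Day 10 pre-dose |

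**Doses on each side of the laboratory baseline**

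- Period 2 Day 10 pre-dose: 9/11 = 81.8% before, 2/11 = 18.2% after.
- If the last sample before the contraceptive is a pre-dose Day 9 draw: 8/11 = 72.7% before, 3/11 = 27.3% after.

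**What the change tables can show**

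Let L(t) be a laboratory value at time t and B the SAP baseline sample.

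- Planned change: L(t) − L(B).
- Change from a drug-free value: L(t) − L(Day -1) = [L(B) − L(Day -1)] + [L(t) − L(B)].

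The planned tables drop the first bracket. The share of the total change they would show once all 11 doses have been given depends on the time course, which the documents do not supply. Under assumed courses:

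| Assumed time course | Share shown |
|---|---|
| Complete by B, then stable | 0% |
| Equal increment per dose | 2/11 to 3/11, about 18–27% |
| Arises wholly after B | 100% |

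On the schedule as read, no Period 2 laboratory sample has a planned change from a drug-free baseline. With a Day -1 baseline, three would (Days 9, 11 and 12).

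**How far Day -1 is from the first PF-06650833 dose**

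- Confinement: Day -1 (1 day) + Period 1 Days 1–3 (3) + Period 2 Days 1–12 (12) = 16 days, matching the stated 16. Day -1 is therefore 4 days before Period 2 Day 1.
- PK blood: 12 time points per period × 12 mL (Protocol Sections 1.3 and 8.4) = 144 mL in Period 1 and 288 mL by Period 2 Day 12, out of about 350 mL in total (Protocol Section 8).

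**The case against.** The best defence is that the secondary objective concerns safety when PF-06650833 is co-administered with the contraceptive, and a last-value-before-contraceptive baseline for the combination phase answers that. It does answer part of it, which is why that baseline should stay. However, PF-06650833 is the investigational product and the contraceptive is not (Protocol Section 6.1). A table that isolates the effect of adding the contraceptive, plus the final PF-06650833 doses, does not show the overall laboratory change on the drug under study.

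Other points on that side:

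- **Day -1 is an imperfect reference.** It precedes the Period 1 contraceptive dose, several days of confinement and about 144 mL of blood sampling, and the study has no control arm. Blood loss could itself move hematology values. This stands, and it calls for a footnote. A labelled, imperfect drug-free reference is still more use than none.
- **No laboratory draw is scheduled on Period 2 Day 1, so vital signs are not a fair model.** The schedule does differ, but the last-measurement rule used in Section 3.4 accommodates this: Day -1 is the last scheduled sample before PF-06650833.
- **The information survives elsewhere.** Absolute summaries, listings, abnormality checks, adverse events and the investigator's laboratory review all remain, there are no hypotheses for safety data, and about 10 participants are enrolled. This limits the severity, but does not make the change tables informative about the drug.
- **The sponsor's reporting standards may define another baseline.** They may, but they are not supplied, and the explicit text of Section 3.4 names only one.
- **The laboratory sentence may be a drafting slip.** The first contraceptive dose is in Period 1, and Day 10 is not the beginning of Period 2. But the vital-signs sentence uses the same wording and the same Day 10 parenthesis for its combination-phase baseline, so Day 10 is the operative reading.

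**Conclusion.** The concern holds. As written, the SAP has no laboratory baseline that precedes PF-06650833, and its change-from-baseline tables cannot show a laboratory effect that is already established and stable when the Day 9/10 sample is drawn. Between 73% and 82% of the PF-06650833 doses fall before that baseline. This dose share is not itself a measure of laboratory effect: the share of any effect shown runs from 0% to 100% with the time course, and the 18–27% figure rests on an assumed equal increment per dose. Effects that emerge after the baseline would still appear.

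This should be fixed because it affects a named secondary endpoint, departs from the treatment of vital signs and ECG in the same section, and leaves the abnormality assessment without a stated reference. It does not touch the primary PK analysis.

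**What to change.** In SAP Section 3.4, add a laboratory baseline defined as the last measurement before the first PF-06650833 dose, which on the current schedule is the Day -1 sample. Then:

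- Summarize laboratory change from that value for the Period 2 samples.
- State in Section 3.5.2 that it is the baseline for the in-range/out-of-range assessment.
- Keep the last value before the Day 10 contraceptive dose as a second baseline for the increment from adding the contraceptive.
- Correct the baseline cross-references in Sections 6.2.2, 6.2.3 and 6.2.4, which point to Sections 3.5.2, 3.5.3 and 3.5.4, so that all three point to Section 3.4, where the definitions are.
- Footnote the new columns: change from Day -1 also reflects the Period 1 contraceptive dose, confinement and PK blood sampling, so it is not a pure PF-06650833 effect.

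The cost is SAP wording and one extra set of change-from-baseline columns. No new sample or visit is needed. The remaining weakness, the uncontrolled 4-day gap between Day -1 and the first PF-06650833 dose, cannot be removed by an analysis change and has to be disclosed.

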3.5. Safety Endpoints

The following data are considered in standard safety summaries (see protocol for collection days and list of parameters):

- *adverse events.*
- *laboratory data.*
- *vital signs data.*
- *ECG results.*

3.5.1. Adverse Events

An adverse event will be considered a Treatment-Emergent Adverse Event (TEAE) if the event started during the effective duration of treatment. All events that start on or after the first dosing day and time/start time, if collected, but before the last dose plus the lag time (28 days) will be flagged as TEAEs. The algorithm will not consider any events that started prior to the first dose date. Any events occurring following start of treatment or increasing in severity and occur in either of the following three phases: OC, PF-06650833 (Days 1-10 of

Period 2), OC+PF-06650833 (Days 10-12 of Period 2), will be counted as treatment emergent. Events that occur in a non-treatment period (for example, Follow-up) will be counted as treatment emergent and attributed to the previous treatment taken.

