- d. **COVID-19 screening:** COVID-19 screening will be done at screening and Day -1. A subsequent COVID-19 test can be performed if participants admitted for residence develop COVID-19 like symptom(s).
- e. **Vital signs (supine BP, pulse rate):** Vital signs will be collected before dosing.
- f. **COVID-19 questionnaire:** Check exposure to positive participant, residence or travel in area of high incidence and COVID-19 related signs and symptoms.
- g. **COVID-19 testing:** The testing for COVID-19 pathogen by PCR will be performed screening and D-1. A subsequent COVID-19 test can be performed if participants admitted for residence develop COVID-19 like symptom(s).
- h. **COVID-19 check temperature:** To be done twice daily during residence.
- i. **OC dosing:** Participants will be dosed with OC following an overnight fast of at least 10 hours. On the day of co-administration of OC and PF-06650833, the two will be administered simultaneously within 5 minutes.
- j. **PF-06650833 QD dosing:** The daily dose of PF-06650833 will be administered at approximately 08:00 ±2 hours.
- k. **OC PK blood sample:** PK blood samples are to be collected at predose, at 30 minutes and 1, 1.5, 2, 4, 6, 8, 12, 24, 36 and 48 hours post OC dose in Periods 1 and 2.
- l. **OC PK blood sample:** The 24 hour OC PK samples on Period 2 Day 11 must be collected pre PF-06650833 dose.
- m. **Period 2:** There is no washout phase between Period 1 and Period 2.
- n. **Follow-up:** Participants will have a telephone contact at least 28 calendar days, and up to 35 calendar days after the last administration of the investigational product(s). At the discretion of the investigator, telephone contact may be substituted with an on-site visit in case of additional follow-up of open AEs or clinically significant laboratory findings

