8.3.1. Time Period and Frequency for Collecting AE and SAE Information

The time period for actively eliciting and collecting AEs and SAEs (“active collection period”) for each participant begins from the time the participant provides informed consent, which is obtained before the participant’s participation in the study (eg, before undergoing any study-related procedure and/or receiving study intervention), through and including a minimum of 28 calendar days, after the last administration of the study intervention.

Follow-up by the investigator continues throughout and after the active collection period and until the AE or SAE or its sequelae resolve or stabilize at a level acceptable to the investigator.

For participants who are screen failures, the active collection period ends when screen failure status is determined.

If the participant withdraws from the study and also withdraws consent for the collection of future information, the active collection period ends when consent is withdrawn.

If a participant permanently discontinues or temporarily discontinues study intervention because of an AE or SAE, the AE or SAE must be recorded on the CRF and the SAE reported using the CT SAE Report Form.

Investigators are not obligated to actively seek information on AEs or SAEs after the participant has concluded study participation. However, if the investigator learns of any SAE, including a death, at any time after a participant has completed the study, and he/she

considers the event to be reasonably related to the study intervention, the investigator must promptly report the SAE to Pfizer using the CT SAE Report Form.

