10.3.1. Definition of AE

AE Definition

• An AE is any untoward medical occurrence in a patient or clinical study participant, temporally associated with the use of study intervention, whether or not considered related to the study intervention.• Note: An AE can therefore be any unfavorable and unintended sign (including an abnormal laboratory finding), symptom, or disease (new or exacerbated) temporally associated with the use of study intervention.

Events Meeting the AE Definition

• Any abnormal laboratory test results (hematology, clinical chemistry, or urinalysis) or other safety assessments (eg, ECG, radiological scans, vital sign measurements), including those that worsen from baseline, considered clinically significant in the medical and scientific judgment of the investigator. Any abnormal laboratory test results that meet any of the conditions below must be recorded as an AE:
• Is associated with accompanying symptoms;• Requires additional diagnostic testing or medical/surgical intervention;• Leads to a change in study dosing (outside of any protocol-specified dose adjustments) or discontinuation from the study, significant additional concomitant drug treatment, or other therapy.• Exacerbation of a chronic or intermittent preexisting condition, including either an increase in frequency and/or intensity of the condition.• New condition detected or diagnosed after study intervention administration, even though it may have been present before the start of the study.• Signs, symptoms, or the clinical sequelae of a suspected drug-drug interaction.• Signs, symptoms, or the clinical sequelae of a suspected overdose of either study intervention or a concomitant medication. Overdose per se will not be reported as an AE or SAE unless it is an intentional overdose taken with possible suicidal/self-harming intent. Such overdoses should be reported regardless of sequelae.

Events NOT Meeting the AE Definition

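### SAP 3.5.1 gives two conflicting treatment-emergence rules for an adverse event that starts before first dose and worsens on treatment

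*SAP*

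**What the plan says.** SAP 3.5.1 opens with a definition based on onset: "An adverse event will be considered a Treatment-Emergent Adverse Event (TEAE) if the event started during the effective duration of treatment". It makes this operational as a start on or after first dosing and before the last dose plus a 28-day lag. It then adds an exclusion: "The algorithm will not consider any events that started prior to the first dose date".

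The following sentence has a different basis. It begins "Any events occurring following start of treatment or increasing in severity and occur in either of the following three phases", names the OC, PF-06650833 and combined phases, and ends "OC+PF-06650833 (Days 10-12 of Period 2), will be counted as treatment emergent". A closing sentence deals with time off treatment: "Events that occur in a non-treatment period (for example, Follow-up) will be counted as treatment emergent", with attribution to the preceding treatment.

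In Protocol 8.3.1, active collection of adverse events "begins from the time the participant provides informed consent". Protocol 10.3.1 lists among the events that meet the AE definition: "Exacerbation of a chronic or intermittent preexisting condition, including either an increase in frequency and/or intensity of the condition". Footnote n of the Schedule of Activities (Protocol 1.3) sets the follow-up: "Participants will have a telephone contact at least 28 calendar days, and up to 35 calendar days after the last administration".

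SAP 6.2.1 leaves AE reporting to sponsor standards that the SAP does not reproduce.

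**The concern.** A TEAE flag has to give one answer for each event. Here an event with pre-dose onset that becomes more severe on treatment gets two. Two programmers working from the same paragraph could produce different TEAE tables and each could point to a sentence in support.

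The stake is the secondary objective, the safety of PF-06650833 given with the OC, for which adverse events are a named endpoint. Worsening on drug is part of what a TEAE table is meant to show. The start-date rule taken alone removes it from that table.

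**Working it through.** The SAP states no figure on this point, so the check is to apply its sentences to each type of event. I take first dose to mean the first OC dose in Period 1, because SAP 3.5.1 lists an OC phase.

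**Start of the window**

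| Case | Start-date definition and exclusion | Severity sentence | Result |
|---|---|---|---|
| 1. Starts after first dose, does not worsen | TEAE | TEAE | Agree |
| 2. Starts in the OC phase, worsens under PF-06650833 | TEAE | TEAE | Agree on status; phase not stated |
| 3. Starts before first dose, does not worsen | Not a TEAE | Not reached | Agree |
| 4. Starts before first dose, worsens in a treatment phase | Not a TEAE | TEAE | **Conflict** |

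Only case 4 conflicts. It follows from the word that joins the two conditions in the severity sentence: onset after start of treatment and increase in severity are alternatives, so the second is not restricted to events that meet the first.

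Case 4 can arise. The Schedule of Activities places consent at the screening visit (Day -28 to Day -2), and collection starts at consent, so up to about four weeks of pre-dose events are recorded.

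Case 2 is a smaller gap. The event is a TEAE either way, but the SAP does not say whether it belongs to the phase in which it began or the phase in which it worsened.

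**Size**

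Protocol 9.5 plans about 10 participants, with at least 8 completing. One participant classified differently moves an incidence by:

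- 1/10 = 10 percentage points with 10 participants
- 1/8 = 12.5 percentage points with 8 participants

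These are upper limits per participant. The proportion with any TEAE does not change if that participant has another TEAE.

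**End of the window**

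Count days from the last dose. The start-date rule requires onset before Day 28. The Follow-up sentence states no limit. The contact falls between Day 28 and Day 35, so the onset days on which the two sentences could differ are:

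- contact on Day 28: Day 28 only, 28 − 28 + 1 = 1 day
- contact on Day 35: Days 28 to 35, 35 − 28 + 1 = 8 days

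**The case against.** The paragraph can be read so that it does not conflict. The severity clause could be meant only for events that begin after first dose and worsen in a later phase, with the specific pre-dose exclusion governing the more general sentence after it. Alternatively, since Protocol 10.3.1 counts an exacerbation as an AE, the worsening could be entered as a new record with an on-treatment start date, which the start-date rule would then flag. Both are sensible conventions. The SAP adopts neither, and Protocol 10.3.1 gives no onset-date convention. If one is intended, stating it is the remedy. Deleting the severity clause would also end the conflict, but without such a recording convention it would leave worsening on drug out of the TEAE tables.

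A reader might infer more than the text supports:

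- **That the worsening vanishes from safety reporting.** It does not. SAP 6.2 summarises all clinical AEs separately from TEAEs and provides participant listings.
- **That TEAE counts are the main safety summary.** The documents do not rank them so; SAP 3.2 names adverse events, laboratory tests and vital signs.
- **That OC-phase events which worsen on PF-06650833 are lost.** They are TEAEs under every sentence; only their phase is open.
- **That there is a fixed eight-day contradiction at follow-up.** Eight days is the maximum and needs a Day 35 contact. The Follow-up sentence can also be read as an attribution rule inside the 28-day lag.

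It is also fair that few events are likely to qualify. Case 4 needs an event that starts in the weeks before dosing, does not lead to exclusion, persists to dosing and then worsens, in healthy participants.

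**Conclusion.** The conflict is real as written, and nothing else in the SAP or Protocol resolves it. It is confined to events that start between consent and first dose and then increase in severity on treatment. The consequence is an ambiguous TEAE table, with at most 10 to 12.5 percentage points per reclassified participant and probably few such participants. The safety summaries are descriptive, with no hypothesis or decision rule (SAP 5.1), and the primary PK analysis is untouched. Even so, this is a stated rule that can give a wrong safety count, and it should be corrected before the analysis.

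The conclusion assumes that a worsening is kept on the original AE record with its original start date; if site practice creates a new record, the conflict has no practical effect. It does not depend on whether first dose means the OC or PF-06650833. The end-of-window point is a minor clarification.

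**What to change.** Replace the pre-dose exclusion and the severity sentence in SAP 3.5.1 with one rule:

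- An event is a TEAE if it starts on or after first dose, or if it starts before first dose and increases in severity on or after first dose.
- It is attributed to the phase in which it starts or, if it worsens later, the phase in which it worsens. This includes events that start in the OC phase and worsen under PF-06650833.

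Remove the unqualified exclusion of events with pre-dose onset. State whether a worsening is a new AE record or a severity change on the existing one, and which product's dose counts as first dose.

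As a minor addition, give one end to the TEAE window for every sentence: either through and including Day 28 after the last dose, or up to the follow-up contact.

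The cost is SAP wording and a small programming change, with no new data. The downside is that TEAE counts may rise slightly.
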